7 STATISTICS AND DATA ANALYSIS

7.1 SAMPLE SIZE CALCULATION

The study will generate a large amount of continuous and categorical data. It is noted that some definitions (long covid, subgroups of post COVID syndromes) are in evolution at present therefore it is difficult to be definitive regarding this. We also note that as well as potential direct cardiovascular symptoms, symptoms of diabetes distress and indeed depression have increased prevalence in the population of people with diabetes (7, 8).

In general, sample size of 526 in each group allows 90% power ($\alpha=0.05$) to detect sizes of 0.2 of a standard deviation (SD) and 85 allows power for differences of 0.5 SD. We plan for recruitment of 500 people after COVID infection with 500 controls and the opportunity to restudy cases (total recruitment 1500), expecting near complete data for questionnaire variables but allowing for reduced numbers of participants for biochemical measures (allowing for remote participation). A sample size of 500 per group would also allow detection of differences in highly prevalent symptoms from 50% to 40% (for example early estimates persistent symptoms after COVID 55% (1)) and for less prevalent symptoms from 20% to 12% (eg estimates of diabetes distress and depression often 10-20%).

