4.2 STUDY DESCRIPTION

We will recruit a large Case-Cohort of people with type 1 and type 2 diabetes in Scotland to assess the prevalence of symptoms after self-reported COVID infection. We will further recruit a nested case control study of those with positive COVID test in the clinical record (cases) and controls to examine physical measures, glycaemia and diabetes complications.

[figure not shown]
The cohort will be recruited predominantly from the NHS Research Scotland Diabetes Research Register with additional direct recruitment invited from clinic lists of those with previous evidence of COVID infection. This cohort will involve self-completed questionnaires and minimal personal information limited to contact details (e-mail, telephone) and not including patient identifiers such as name, address or CHI. The cohort will acknowledge “By ticking this box, you acknowledge that you have read the PIS and have had the opportunity to ask any and all questions to a research staff member” electronic checkbox prior to completion of demographic information and questionnaires.

The Nested Case Control study will be conducted in person under written consent and include:

[figure not shown]
- Blood sampling (for biomarkers and routine clinical measurements)
- Physical tests (incremental walk test, grip strength test)
- Waist and thigh measurement
- Bioimpedance measurement
- Pulmonary function test

Cases will repeat the CRF study visit approximately 1 year from the baseline visit.

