4.5 STUDY ASSESSMENTS

Case-Cohort:

Self-completed, offered online (can be offered by phone/on paper for participants who request this).

1. Demographics
2. Questionnaires (in order of priority)
 - a. Wellcome Trust COVID 19 questionnaire (Most up to date version in use at the time of the study): This is a comprehensive instrument covering physical, cognitive, and mental health domains and will also allow comparison to developing UK reference population data). Questions deemed to require additional support have been removed.
 - b. Diabetes Related Quality of Life (DQOL)

- c. Diabetes-Specific [name]-1
 - d. EQ5D
3. Option to self-nominate for nested case control study.

Nested Case Control (CRF visit):

1. Written consent
2. Questionnaires (if not done previously) or Update of symptoms score Wellcome questionnaire section 1.3
3. Blood sample (optional) for research labs (16ml total, 6ml purple top (EDTA), 6ml gold top (serum), 4ml blue top (citrate)) for non-routine bloods: inflammatory (e.g. CRP), vascular (t-PA, vWF) and cardiac (hs troponin, NT proBNP) biomarkers consistently predictive of long-term adverse outcomes.
4. Blood sample (8ml total, 3ml purple top (EDTA) and 5ml gold top (serum)) for routine clinical measures (HbA1c, LFTs, lipids, U&Es).
5. Physical measures
 - a. Incremental walking test
 - b. Grip strength
6. Waist and thigh measurement
7. Bioimpedance (optional if site does not have this equipment)
8. Pulmonary function test (optional if site does not have this equipment)

Cases will be invited to a repeat study visit 1 year (40 to 64 weeks) from the initial study visit.

SOPs (shared from other studies) will be used to standardise:

- Incremental walk test
- Grip strength test
- Blood sampling, storage and shipment
- Pulmonary function test

Clinical data: Baseline and follow up data from SCI-Diabetes including glucose control and blood pressure.

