2. **Other questionnaire data:** diabetes depression score, DQOL all of which are assessed currently only and will be assessed in cohort vs control
3. **Walk test**
4. **Hand grip**
5. **Pulmonary function measures eg. FEV1**

Comparison of cases vs COVID positive cohort for demographics and main study measures.

Case vs control (First and second visit data)

1. **Frequency of COVID symptoms** (derived from question 1.3 Wellcome questionnaire: 28 domains answering yes/no for 0-28 score and by self-report at time of infection at 3 month, at time of first questionnaire, first visit and at second visit).
 - a. **Primary analysis:** second visit score case vs control (first visit) with adjustment for age, sex, ethnicity, sex, type of diabetes, SIMD
 - b. Secondary analyses:
 - i. within cohort comparison of time of infection vs all time points
 - ii. comparison time of infection and 3 months vs current score of control (with adjustment)
2. **Other questionnaire data:** diabetes depression score, DQOL all of which are assessed first and second visit cohort vs control (first visit)

3. **Walk test** first and second visit cohort vs control (first visit)
4. **Hand grip** first and second visit cohort vs control (first visit)
- Pulmonary function measures eg. FEV1** first and second visit cohort vs control (first visit)

B. Screening log. As above contain patient identifiers, will be held on NHS computers.

Output - acceptance rate for study

C. Study data - will be held within Redcaps platform. Outputs: process data on completion of the different modules of the study, final study dataset.

Key aspects will be

- a. Record of consent and electronic consent
- b. Ability to enter data to personal computer/ smartphone by participant
- c. Ability to enter separate data under same study ID for study visit
- d. Cloud exportable to SAS/ SPSS/ R

Analyses will be carried out by the study team using the statistical support offered by the University of Glasgow.

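### The one-year symptom score is collected only at the in-person repeat visit, so a case who does not return has no score, although section 7.1 expects near-complete questionnaire data

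*Protocol*

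**What the plan says.** **Sample size (Protocol 7.1).** The plan is for "500 people after COVID infection with 500 controls and the opportunity to restudy cases (total recruitment 1500"). Since 1500 = 500 + 500 + 500, every case is counted again at the restudy. The same sentence describes the data as "expecting near complete data for questionnaire variables but allowing for reduced numbers of participants for biochemical measures (allowing for remote participation").

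**Nested study (Protocol 4.2, 4.4, 4.5).** "The Nested Case Control study will be conducted in person under written consent and include" blood sampling, physical tests and other measurements. The repeat of Wellcome section 1.3 is a row of the visit matrix in 4.4, marked at week 0 and at one year, and an item of the visit list in 4.5. On follow-up, 4.5 says: "Cases will be invited to a repeat study visit 1 year (40 to 64 weeks) from the initial study visit".

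**Remote completion (Protocol 4.4, 4.5, 5.2).** Online, phone and paper completion is described under the case cohort, as a single completion at any time.

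**Analysis (Protocol 7.2).** In the block for first and second visit data, the primary analysis is "second visit score case vs control (first visit) with adjustment for age, sex, ethnicity, sex, type of diabetes, SIMD".

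**Replacement (Protocol 5.6).** Controls who do not complete the required tests may be replaced. Nothing is said about cases who miss the one-year visit.

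**The concern.** The one-year score exists only for cases who attend a second time. Attendance means travelling to the facility and, as scheduled, doing an incremental walk test and a grip test. The score measures current symptoms, so the same symptoms may influence who returns. Cases who are still unwell may stay away, which would understate persistent symptoms. Cases who have recovered may lose interest, which would overstate them.

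The score itself needs no equipment and no visit. The protocol already collects the same questionnaire remotely in the cohort. Tying it to the visit at one year makes the questionnaire outcome as vulnerable to loss as the physical tests, which is not what section 7.1 expects of questionnaire data.

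**Working it through.** **1. Inputs from the protocol (7.1).** Alpha 0.05, power 90%, differences of 0.2 SD and 0.5 SD, 500 per group, and 50% versus 40% for a common symptom. Sidedness is not stated; two-sided is assumed. No return rate at one year is given.

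**2. The plan's own figures.** n per group = 2 × (1.960 + 1.282)² / d².
- d = 0.2: 525.4, rounded up to 526. The protocol says "sample size of 526 in each group allows 90% power".
- d = 0.5: 84.06, rounded up to 85. The protocol says "85 allows power for differences of 0.5 SD".

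Both reproduce. With 500 per group, power is 88.5% for 0.2 SD and 89.0% for 50% versus 40%.

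**3. Is there a route to a one-year score without a visit?** The nested study is in person (4.2). Section 1.3 at one year appears only in the visit matrix (4.4) and the visit list (4.5). The remote modes are set out for the cohort (4.5, 5.2). The analysis names the second-visit score (7.2). No other route is described.

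**4. Loss of numbers (assumed return rate r).** With 500 controls and 500r cases, power = Φ(0.2 / √(1/500 + 1/(500r)) − 1.960):

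| r | cases | power for 0.2 SD |
|---|---|---|
| 1.0 | 500 | 88.5% |
| 0.9 | 450 | 86.8% |
| 0.8 | 400 | 84.6% |
| 0.7 | 350 | 81.9% |

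The loss of power is moderate.

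**5. Selective return (assumed r and odds ratio).** Let the one-year score be standard normal and let return follow a logistic model with odds ratio OR per SD of higher score. The intercept is solved to give overall return r, and the bias is the mean score among returners. A close approximation is ln(OR) × (1 − r). For OR 0.8 and r = 0.8 this is −0.223 × 0.2 = −0.045 SD; numerical integration gives −0.044 SD. As a share of the target, 0.044 / 0.2 = 22%.

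| r | OR 0.9 | OR 0.8 | OR 0.7 |
|---|---|---|---|
| 0.9 | −0.011 SD (5%) | −0.022 SD (11%) | −0.035 SD (18%) |
| 0.8 | −0.021 SD (10%) | −0.044 SD (22%) | −0.070 SD (35%) |
| 0.7 | −0.032 SD (16%) | −0.066 SD (33%) | −0.104 SD (52%) |

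Percentages are of the 0.2 SD target. With odds ratios above 1 the sign reverses.

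**6. Prevalence scale (assumed).** Suppose true one-year prevalence is 50%, symptomatic cases return at 60% and others at 80%, so overall return is 70%. Observed prevalence = 0.5 × 0.6 / (0.5 × 0.6 + 0.5 × 0.8) = 0.30 / 0.70 = 43%. With the two rates exchanged it is 0.40 / 0.70 = 57%. The shift of about 7 points compares with the 10-point difference in 7.1.

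**The case against.** Several points on the other side stand.

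- **No direct contradiction in 7.1.** A reader might infer that 7.1 promises near-complete questionnaire data *because* participation is remote, and so contradicts 4.2. Grammatically, the parenthesis on remote participation explains the reduced biochemical numbers. Section 7.1 also states no separate power for one year and speaks only of an opportunity to restudy.
- **The study's primary objective is not lost.** A reader might infer that the primary question goes unanswered. The synopsis assigns it to the case cohort, which has remote completion and its own analysis. Only the first-and-second-visit block is touched, and "primary" is a label within that block.
- **Bias is not established.** Return rate, odds ratio and direction are all assumed. Enrolled cases have already managed one visit, and spirometry is optional, so the burden argument rests mainly on travel and the walk test.
- **Remote completion is not forbidden.** Section 6.2 lists a self-filled questionnaire separately from the visit data, and RedCap accepts direct entry by participants.
- **Missing scores can be left to the analysis plan.** Section 7.2 announces one, and earlier scores from the same cases could inform it. The protocol does not prescribe an analysis of attenders alone.

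The last two do not remove the point. An analysis plan can model a score that was never collected, but cannot collect it. If loss depends on unobserved one-year symptoms, earlier scores may not correct for it. And a route that is merely not excluded is not a scheduled one.

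**Conclusion.** The point holds for the one-year analysis of the nested study only. As scheduled, a case who does not return has no one-year score, and this fits poorly with a plan that expects near-complete questionnaire data and counts all 500 cases again. The comparison may be biased in either direction. At an assumed 80% return and odds ratio of 0.8 per SD, the bias is about 0.04 SD, 22% of the 0.2 SD target. It ranges from roughly 5% to 52% over 70–90% return and odds ratios of 0.7–0.9. These figures take no account of covariate adjustment or of the use of earlier scores. The cohort primary analysis and the first-visit nested analysis are not affected, and 526 and 85 are correct. This is a design weakness that is cheap to reduce, not an error of calculation.

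**What to change.** - **Sections 4.4 and 4.5:** offer the one-year Wellcome section 1.3 to every enrolled case by RedCap link at 40 to 64 weeks, with phone or paper on request, whether or not they attend. Keep the walk test, grip, spirometry and bloods at the visit.
- **Section 7.2:** define the one-year score as the score from all enrolled cases by any mode, record the mode, and report attenders only as a sensitivity analysis.
- **Section 7.1:** state that near-complete questionnaire data at one year relies on this route.

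**Cost.** A modest protocol amendment and one survey link. RedCap already takes direct entry, and an e-mail address and/or telephone number is held after written consent (6.2). The downsides are a mixed mode of completion, some staff time for phone or paper returns, and non-response that will remain and may still relate to symptoms.

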7.2 PROPOSED ANALYSES

An analysis plan will be prepared for the University of Glasgow Research Data Management department before the study closes, to detail what analysis will be performed on the data.

Case cohort study:

This includes **participant completed questionnaires only**. We will not have access to clinical record for whole group (limited to those in nested study) and will rely on patient self-report of COVID testing and infection to create groups. Analysis will be in three groups:

- a. Test positive COVID declared (**cohort A**)
- b. no test but self-declared COVID (**cohort B**)
- c. no COVID infection declared, including those with suspected infection but test negative (**control**)

Analysis of this data will include

1. **Frequency of COVID symptoms** (derived from question 1.3 Wellcome questionnaire: 28 domains answering yes/no for 0-28 score and by self-report at time of infection at 3 months and current (>3 months)).
 - a. **Primary analysis:** current score cohort vs control with adjustment for limited demographic panel: age band, ethnicity, sex, type of diabetes
 - b. Secondary analyses:
 - i. within cohort comparison of time of infection vs 3 months vs current
 - ii. comparison time of infection and 3 months vs current score of control (with adjustment)
2. **Other questionnaire data:** diabetes depression score, DQOL all of which are assessed currently only and will be assessed in cohort vs control.
3. Comparison of above end points in cohort B to cohort and controls.

NESTED CASE CONTROL STUDY

For this data, consent will allow access to confirm that patient is COVID test positive in the clinical record. Definitions and comparison will therefore be between:

Cases - COVID test positive in clinical record

Control - no previous clinical COVID infection reported by patient, no record positive COVID test.

Case vs control (First visit)

1. **Frequency of COVID symptoms** (derived from question 1.3 Wellcome questionnaire: 28 domains answering yes/no for 0-28 score and by self-report at time of infection at 3 months and current (>3 months)).
 - a. **Primary analysis:** current score case vs control with adjustment for age, sex, ethnicity, sex, type of diabetes, SIMD
 - b. Secondary analyses:
 - i. within cohort comparison of time of infection vs 3 months vs current
 - ii. comparison time of infection and 3 months vs current score of control (with adjustment)
 - iii. relationship of cycle threshold to symptom scores
2. **Other questionnaire data:** diabetes depression score, DQOL all of which are assessed currently only and will be assessed in cohort vs control
3. **Walk test**
4. **Hand grip**
5. **Pulmonary function measures eg. FEV1**

Comparison of cases vs COVID positive cohort for demographics and main study measures.

Case vs control (First and second visit data)

1. **Frequency of COVID symptoms** (derived from question 1.3 Wellcome questionnaire: 28 domains answering yes/no for 0-28 score and by self-report at time of infection at 3 month, at time of first questionnaire, first visit and at second visit).
 - a. **Primary analysis:** second visit score case vs control (first visit) with adjustment for age, sex, ethnicity, sex, type of diabetes, SIMD
 - b. Secondary analyses:
 - i. within cohort comparison of time of infection vs all time points
 - ii. comparison time of infection and 3 months vs current score of control (with adjustment)
2. **Other questionnaire data:** diabetes depression score, DQOL all of which are assessed first and second visit cohort vs control (first visit)

3. **Walk test** first and second visit cohort vs control (first visit)
4. **Hand grip** first and second visit cohort vs control (first visit)
- Pulmonary function measures eg. FEV1** first and second visit cohort vs control (first visit)

B. Screening log. As above contain patient identifiers, will be held on NHS computers.

Output - acceptance rate for study

C. Study data - will be held within Redcaps platform. Outputs: process data on completion of the different modules of the study, final study dataset.

Key aspects will be

- a. Record of consent and electronic consent
- b. Ability to enter data to personal computer/ smartphone by participant
- c. Ability to enter separate data under same study ID for study visit
- d. Cloud exportable to SAS/ SPSS/ R

Analyses will be carried out by the study team using the statistical support offered by the University of Glasgow.

Output will include locked data set, written report, manuscript, presentation of findings to Scottish Diabetes Group (SDG) and widespread dissemination of results via the existing infrastructures within the Scottish diabetes community. In addition, given the use of resources such as the Wellcome COVID questionnaire we would expect to contribute to shared data analysis more widely. Long term data storage will be with the University of Glasgow Enlighten system and access to bona fide researchers to data stripped of contact details and identifiers.

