2. **From diabetes clinic lists or database search (SCI Diabetes):** To augment recruitment of COVID test positive participants we will also screen clinic lists and recruit directly. A member of the study team will screen diabetes clinic lists (eg trak or local clinical system, when possible SCI Diabetes) which routinely have a note of previous COVID infection. Name and CHI noted on screening log (excel spreadsheet held on NHS computer). If patient declines this is noted and no further action. If patient assents to contact then contact information taken (telephone and email – if neither possible postal address) and added to screening log. Electronic data collection link sent by preferred means. If electronic remote data collection not possible then paper questionnaires will be made available by post or study team will discuss over the phone. Cases identified to by SCI Diabetes search will be approached in writing with Caldicott Guardian approval in place within a Health Board (likely to be used in selected Health Boards only).
3. We will also advertise the study by leaflets and posters and via newsfeed to My Diabetes My Way, allowing self-referral to the study team.

NESTED CASE-CONTROL RECRUITMENT:

Cases, by definition, will have had a positive COVID test present on the clinical record. Potential cases will be selected from the cohort where a record of self-reported COVID infection is presented. Potential cases will be invited to CRF visit by telephone or email. Where assent is given by phone the clinical record will be checked to confirm positive COVID test, visit is arranged, and PIS sent. All other study procedures will take place only after face-to-face written consent is obtained at the CRF visit.

Controls will be selected from the pool of people who have completed the online questionnaire information and who have indicated that they have not had a **positive** COVID test and do not believe that they have had COVID infection. Those who had possible infection but subsequent test negative are included. Matching will be by age (5 year category),

ethnicity, sex, SIMD quintile and type of diabetes included in the participant completed questionnaire.

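### Section 7.2 calls three different symptom-score contrasts the primary analysis, while the synopsis has one primary question, in the case cohort, and makes the nested study secondary

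*Protocol*

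**What the plan says.** Protocol section 7.2 has three analysis blocks. Each opens with the 0-28 score from Wellcome question 1.3 and marks one contrast as the primary analysis:

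1. Case cohort: "current score cohort vs control with adjustment for limited demographic panel: age band, ethnicity, sex, type of diabetes".
2. Nested study, first visit: "current score case vs control with adjustment for age, sex, ethnicity, sex, type of diabetes, SIMD".
3. Nested study, first and second visits: "second visit score case vs control (first visit) with adjustment for age, sex, ethnicity, sex, type of diabetes, SIMD".

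Section 7.2 does not say which of the three is the study's primary analysis.

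The synopsis does rank the two components. Its primary objective is assigned to the case cohort, and the outcome is how common longer-term symptoms are up to two years after infection. The nested study is the secondary objective, with incremental walking test, hand grip and HbA1c. The symptom score is not among the nested outcomes there. Section 3 repeats the two objectives without naming the component each belongs to.

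Section 7.1 gives the only alpha: "sample size of 526 in each group allows 90% power ($\alpha=0.05$) to detect sizes of 0.2 of a standard deviation". It also states "We plan for recruitment of 500 people after COVID infection with 500 controls and the opportunity to restudy cases". The synopsis and section 4.9 attach those 500 + 500 to the nested study.

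**The concern.** The protocol points in two directions about its main result. The synopsis points to a prevalence in the case cohort. Section 7.2 points to three score comparisons, two of them in the component that the synopsis calls secondary. The sample size is also set for the nested study.

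The three contrasts could disagree. Cohort groups rest on self-report, whereas nested cases need a positive test in the clinical record. SIMD is an adjustment variable only in the nested contrasts. The third contrast compares scores taken roughly a year apart (40 to 64 weeks, section 4.4), because controls are not restudied. If one contrast is clearly positive and another is null, section 7.2 lets either be reported under the primary label.

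**Working it through.** **Step 1: reproduce the plan's figures.** For two means with two-sided alpha 0.05 and 90% power, n per group = 2(1.960 + 1.282)² / d².
- d = 0.2: about 525.4, rounded up to 526, as stated.
- d = 0.5: about 84.1, rounded up to 85, as stated ("85 allows power for differences of 0.5 SD").

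So 0.05 is the two-sided alpha for one two-group comparison.

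**Step 2: independence bound.** Three tests at 0.05: 1 − 0.95³ = 14.3%. Two tests: 1 − 0.95² = 9.75%.

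**Step 3: why independence cannot hold.** Contrasts 2 and 3 use the same cases and the same first-visit control scores. With equal group sizes and variances, and correlation rho between a case's two visits, the correlation between these contrasts is (1 + rho)/2, which is at least 0.5 when rho is not negative. The nested sample also comes from the online sample (section 5.1): "Potential cases will be selected from the cohort where a record of self-reported COVID infection is presented". Controls are likewise drawn from those who completed the online questionnaire. Let r be the within-person correlation between questionnaire and first visit, and let the cohort be M times the nested sample in each arm. Then:
- corr(1, 2) = r/√M
- corr(1, 3) = (rho + r)/(2√M), taking the questionnaire-to-second-visit correlation as rho
- corr(2, 3) = (1 + rho)/2

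The protocol gives none of r, rho or M. They are assumptions, so ranges are shown.

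**Step 4: chance of at least one |z| > 1.96 when all three null hypotheses are true** (2 million trivariate normal draws per cell):

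| M | r 0.95, rho 0.8 | r 0.9, rho 0.7 | r 0.8, rho 0.5 | r 0.7, rho 0.3 |
|---|---|---|---|---|
| 1 | 8.1% | 9.1% | 10.5% | 11.6% |
| 2 | 10.3% | 10.8% | 11.7% | 12.4% |
| 5 | 11.2% | 11.6% | 12.3% | 12.8% |
| 10 | 11.4% | 11.9% | 12.5% | 13.0% |

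The range is 8.1% to 13.0%, or 1.6 to 2.6 times 0.05. Even with contrast 1 taken as independent of the other two and rho = 0, the figure is 13.7%. The two nested contrasts alone give 7.1% (rho 0.8) to 9.0% (rho 0).

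**Step 5: two ways to resolve it.**
- One primary contrast at 0.05: a comparison with 500 per group has 88.5% power for 0.2 SD.
- All three kept as primary with a Bonferroni split (0.05/3 = 0.0167): power at 500 per group falls to 77.9%, and 90% power needs 676 per group.

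**The case against.** The best defence is that each label means primary for this outcome within this block. Each one is item 1a in its own block and is followed by secondary analyses at 1b. The synopsis then supplies the order across blocks. This is a plausible reading, and it defeats the stronger inference that the protocol has no deciding component at all: the gap is in 7.2, and the synopsis partly fills it. But the protocol nowhere states the within-block meaning, and the 500 + 500 sample size pulls towards the nested study.

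A second defence is that alpha splits and testing order belong in the analysis plan, which section 7.2 promises and which is not shown. That stands, and their absence is not held against the protocol. What remains is a conflict between two pieces of stated text.

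A third is that 0.05 is a sample-size input in an observational study whose primary outcome is an estimate. That also stands. A reader might infer that the study promises a 5% study-wise error rate and breaks it, but no such promise is made. A reader might also take 14% as the error rate; shared participants rule that out.

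Finally, one might conclude that fixed-order testing is required and that everything else in 7.2 should be called exploratory. The document does not support this: the synopsis names walk test and hand grip as secondary outcomes, and a testing order is a design preference.

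**Conclusion.** Wrong as written, as an internal contradiction. Section 7.2 has three primary analyses, two of them in a component that the synopsis ranks as secondary. None of the three estimates the prevalence that the synopsis names as the primary outcome.

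If any of the three could be claimed as primary at 0.05, the chance of at least one false-positive primary result is about 8% to 13%. This assumes that all three nulls are true, equal arms, within-person correlations of 0.7 to 0.95 (questionnaire to first visit) and 0.3 to 0.8 (between visits), and a cohort one to ten times the nested sample. The contradiction in labels does not depend on these assumptions; only the size does.

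**What to change.** In section 7.2, keep the study-level label *Primary analysis* for the case cohort only. Reconcile it with the synopsis by stating that the primary outcome is the prevalence of longer-term symptoms after infection, with the adjusted current-score contrast against controls as its stated comparison. Relabel the nested first-visit and second-visit score contrasts as secondary. Leave walk test, hand grip and HbA1c as secondary, as the synopsis has them. A fixed testing order for the secondary score contrasts is optional and can go in the analysis plan.

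This changes wording only: no extra participants, visits or data. The downside is that a nested symptom-score result, including the one based on record-confirmed infection, can no longer be presented as the study's primary result.
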